- ALT = alanine aminotransferase; aPTT = activated partial thromboplastin time; AST = aspartate aminotransferase; INR = international normalized ratio; CrCl = creatinine clearance; GFR = glomerular filtration rate; PT = prothrombin time; ULN = upper limit of normal.
- a. Criteria must be met without packed red blood cell (pRBC) transfusion within the prior 2 weeks. Participants can be on stable dose of erythropoietin (≥ approximately 3 months).
- b. Creatinine clearance (CrCl) should be calculated per institutional standard.
- Note: This table includes eligibility-defining laboratory value requirements for treatment; laboratory value requirements should be adapted according to local regulations and guidelines for the administration of specific chemotherapies.
 - 11. Participants with controlled (treated) hepatitis B virus (HBV) infection will be allowed if they meet the following criteria:
 - Antiviral therapy for HBV must be given for at least 4 weeks and HBV viral load must be less than 500 IU/mL prior to first dose of study intervention.
 - Participants on active HBV therapy with viral loads under 500 IU/ml should stay on the same therapy throughout study treatment.
 - Participants who are anti-HBc (+), negative for HBsAg, negative for anti-HBs, and have an HBV viral load under 500 IU/mL that do not require HBV antiviral prophylaxis.
 - 12. Participants may have a past or ongoing hepatitis C virus (HCV) infection. Participants must have completed their treatment at least 1 month prior to W1D1 or have received at least 1 month of direct acting antiviral (DAA) HCV therapy with no DAA related safety events and stable LFTs. For participants not on anti-HCV therapy at the time of study enrollment, DAAs for treatment of HCV infection can be initiated per the investigator's discretion, if LFTs are stable after 3-6 months of study intervention upon sponsor consultation.
 - 13. Provision of recent tumor tissue (as defined below) is mandatory at screening. Exceptions will be accepted for participants with no recent baseline tumor tissues after documented discussion and approval by the sponsor.
 - Tumor tissue obtained within 180 days of enrollment and after the last dose of most recent anti-cancer therapy.
 - Or a new biopsy.

Sex

- 14. Male and/or female who meet the requirements for contraception and breastfeeding as follows (additional contraception guidance is provided in Appendix 4, Section 10.4.2):

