6.6 Dose Modification

Based on the known toxicity profiles of regorafenib and pembrolizumab, certain AEs are likely to be associated with one drug versus the other. For example, treatment-emergent hypertension and HFSR are likely to be associated with regorafenib rather than pembrolizumab; similarly, immune-related AEs are likely to be associated with pembrolizumab rather than regorafenib. However, some drug-related AEs such as rash, diarrhea, abnormal thyroid function, and fatigue are overlapping. Therefore, it is important to evaluate each AE and consider time of onset, perform the appropriate work-up for etiology or exclude other causes in order to determine proper management of the adverse reaction and action regarding study treatment. A careful decision should be made by investigators based on all clinical information, e.g., relatedness to study medications.

Dose modifications of regorafenib and pembrolizumab will be based on the highest grade of AE that occurred since the last contact. If a participant experiences multiple toxicities, dose modification will be based on the toxicity with the highest grade. In case of multiple toxicities of the same grade, the investigator may modify the dose based on the toxicity that appears most likely related to study interventions.

In case of dose delays, assessments should be performed on Day 1, according to the SoA (see Section 1.3).

Regorafenib dose modifications should be done according to Table 6–2.

The recommendations regarding dose adjustments and treatment interruptions from Table 6–3 to Table 6–8 can be used as support for the clinical decision and respective monitoring/ treatment guidance. A careful decision will be made by investigators based on all clinical information, e.g. relatedness to study medications.

Once a dose reduction of regorafenib has been performed, there will be no intra-participant reescalation.

Where it is indicated to reduce regorafenib one dose level, Table 6–2 should be followed:

BAY 73-4506 / 21469 08 JUN 2021

Page 59 of 141

Table 6-2: Regorafenib Dose Reduction Scheme

		Daily Regorafenib (3 weeks on, 1 week off)
Current Dose	90 mg	120 mg
Dose Level -1	60 mg	90 mg
Dose Level -2	Not applicable	60 mg

Table 6-3: Dose Modification Guidance, Non-immune Toxicities

Event	Regorafenib	Pembrolizumab
Hematologic toxicities		

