G3/4 Neutropenia G3/4 Anemia G3/4 Thrombocytopenia	 Hold until recovery to ≤ G2 and reduce 1 dose level^a 1st re-appearance: Hold until recovery to ≤ G2 and reduce 1 additional dose level^a 2nd re-appearance: discontinue 	 G3 (excluding G3 neutropenia): Hold and restart at same dose if resolution to ⊆ G1 or baseline ≤ 12 weeks of last infusion Hold and consider discontinuation if NO resolution ≤ 12 weeks of last infusion G4: discontinue^b
Non-hematologic toxicities		
General guidance for G2 events	No modifications	 Consider withholding for persistent symptoms Restart at same dose if resolution to ≤ G1 or baseline ≤ 12 weeks of last infusion Consider discontinuation if NO resolution ≤ 12 weeks of last infusion^b
General guidance for G3 events	 Hold until recovery to ≤ G2 and restart at same dose level or reduce 1 dose level^a (at the investigator's discretion) 1st + 2nd re-appearance: Hold until recovery to ≤ G2 and reduce 1 dose level^a (at the investigator's discretion) 3rd re-appearance: Discontinue Discontinuation is required for gastrointestinal perforation or fistula Hold until recovery in case of cardiac ischemia and/or infarction. At the investigator's discretion restart at same dose level or reduce 1 dose level^a. Permanently discontinue if there is no resolution. 	 Hold and restart at same dose if resolution to ≤ G1 or baseline ≤ 12 weeks of last infusion Hold and discontinue if NO resolution ≤ 12 weeks of last infusion^b
General guidance for G4 events	 Hold until recovery to ≤ G2 and reduce 1 dose level 1st re-appearance: Hold until recovery to ≤ G2 and reduce 1 additional dose levela 2nd re-appearance: Discontinue Discontinuation is required for gastrointestinal perforation or fistula Hold until recovery in case of cardiac ischemia and/or 	Discontinue ^b

Table 6-3: Dose Modification Guidance, Non-immune Toxicities

Event	Regorafenib	Pembrolizumab
	infarction. At the investigator's discretion restart at same dose level or reduce 1 dose level ^a . Permanently discontinue if there is no resolution.	
Specific guidance for I	nand-foot skin reaction (HFSR)	•
G1	Maintain dose level and institute supportive measures immediately for symptomatic relief	No modification

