6.6.2 Dose Modification and Management of Liver Toxicity

Elevation of liver enzymes could be a very common finding during the course of regorafenib and pembrolizumab combination therapy. In the ongoing 19497 study of regorafenib and pembrolizumab in HCC patients in first line, as of 06 JAN 2020, 31% of the patients experienced Grade 3 treatment-emergent AE (TEAE) of AST or ALT increase and 6% of them experienced Grade 4 occurrences.

A careful assessment should be done to define the proper etiology of any hepatic alteration found in the course of the study in order to exclude the underlying disease and an immune-mediated hepatic events as possible causes, before defining a liver toxicity as related to the study interventions.

Participants with a history of HBV or HCV with elevated transaminases who meet the criteria below should be evaluated for viral exacerbation/reactivation and viral load and hepatitis serologies (as needed) should be performed for evaluation of viral exacerbation/reactivation:

- Among participants with baseline AST/ALT ≤2×ULN: AST/ALT >5×ULN
- Among participants with baseline AST/ALT >2×ULN: AST/ALT >3×the baseline level
- AST/ALT >500 U/L regardless of baseline level

Page 65 of 141

Table 6–5: Dose Modification Guidance; Specific Guidance for Liver Toxicity

Event	Regorafenib	Pembrolizumab
General instructions:		
If any of below outlined events will occur	r: Monitor liver function tests weekly or more frequently until re	ecovery to baseline or stabilization
• The recommendations regarding dose adjustments and treatment interruptions can be used as support for the clinical decision. A careful decision will be		
made by investigators based on all clinic	cal information, e.g. relatedness to study medications	
 Follow the guidance provided in Table 6 	-6 with respect to Hepatitis B flare, Hepatitis C recurrence or	flare and immune-related hepatitis
 For any G3/4 increases in ALT/AST or b 	oilirubin:	
 If the increases are primarily seen under ongoing regorafenib treatment (e.g. last pembrolizumab infusion was given one week before): Closely monitor for potential de-challenge, i.e. whether a decrease in ALT/AST and/or bilirubin values is seen within 3 days of regorafenib interruption 		
	s seen and/or a further deterioration in liver function is seen: A	dminister corticosteroids (initial dose of 1-2 mg/kg
prednisone or equivalent) for		
	: Directly follow guidance provided in Table 6–6.	

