- Infection needs to be ruled out with cultures of blood, urine, and ascites (if possible), as well as chest X-ray and abdominal imaging if relevant. If an infection is found, antibiotics should be started
- If t-bilirubin is elevated above baseline, magnetic resonance cholangio-pancreatography or ultrasound with Doppler should be obtained to rule out vascular compromise, biliary obstruction, and/or tumor progression.
- If biliary obstruction is present, consultation with a gastroenterologist and/or an interventional radiologist should be obtained to see if the obstruction may be relieved.
- A careful review of drugs, including herbal and alternative medications, should be obtained, and alcohol use should be ruled out.
- Hepatitis C-infected participants (including participants who previously achieved sustained

Page 68 of 141

Table 6–6: Guidance on Assessment and Further Dosing Following Occurrence of Hepatic Events of Clinical Interest

virological response [SVR] for 12 consecutive weeks after the cessation of antiviral treatment [SVR 12]): Measure HCV RNA viral load.

 Hepatitis B-infected participants: HBV DNA, HBsAg, HBeAg, anti-HBc (total and IgM), anti-HBe, and anti-HBs; participants should be questioned about compliance with the use of antiviral agents

Further information concerning Hepatitis B Flare

Hepatitis B flares are characterized by rapid elevations of ALT and AST to >5 × ULN and/or >3 × baseline. ALT elevation to ≥10 × ULN is common. In the absence of hepatic decompensation, ALT/AST elevations are typically isolated (i.e., limited/no elevations of bilirubin/ALP). Participants who are compliant with antiviral therapy should have continued suppression of HBV DNA at the time of flare; thus, detection of HBV DNA should prompt questioning of participants for compliance. Laboratory abnormalities secondary to flare are typically observed for 3-5 weeks.

Among participants with HBV, a flare should be considered if this pattern is observed and there is no evidence of an alternative etiology. Guidelines for participants with a diagnosis of HBV flare are as follows:

- Care should be instituted in consultation with a hepatologist.
- For participants who have detectable HBV DNA, re-institute antiviral therapy.

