- If the participant is clinically stable, pembrolizumab dosing may be interrupted for up to 12 weeks. Participants should undergo weekly laboratory tests including: AST, ALT, ALP, Tbil, Dbil, INR, HBsAg, HBV DNA (if detected at the onset of the flare). Obtain anti-HBe, anti-HBs, and HBV DNA levels (if not detected at the onset of the flare) every 2-3 weeks.
- Restart pembrolizumab intervention only if ALT returns to normal or Grade 1 (if normal at baseline), or to baseline grade (if Grade 2 at baseline) within 12 weeks, and the participant is clinically stable, otherwise the participant should be permanently discontinued.

Further information concerning Hepatitis C Recurrence or Flare

Participants who achieved SVR 12 and participants with ongoing HCV infection are eligible for enrollment. In rare circumstances, HCV participants who achieve SVR 12 may relapse at later time points. Relapse is characterized by detection of HCV RNA, often accompanied by ALT elevations to >5 × ULN. In the absence of hepatic decompensation, ALT/AST elevations are typically isolated (i.e., limited/no elevations of bilirubin/ALP).

Among participants with uncontrolled hepatitis C, virologic flares are possible. Hepatitis C flares are characterized by rapid elevations of ALT and AST to >5 × ULN and/or >3 × baseline along with a rise in HCV RNA. ALT elevation to ≥10 × ULN and a 1 log elevation in HCV RNA level are common. In the absence of hepatic decompensation, ALT/AST elevations are typically isolated (i.e., limited/no elevations of bilirubin/ALP). Laboratory abnormalities secondary to flare or recurrence are typically observed for 3-5 weeks.

Guidelines for participants with recurrent HCV infection or an HCV flare are described below:

- Interrupt pembrolizumab intervention for up to 12 weeks
- Restart pembrolizumab intervention only if ALT returns to normal or G1 (if normal at baseline), or to baseline grade (if G2 at baseline) within 12 weeks, and the participant is clinically stable, otherwise, the participant should be permanently discontinued

Recurrent HCV infection (relapse of HCV infection for participants successfully treated or with new HCV infection):

If the participant entered the study with an HCV RNA test of "Target not Detected" and has confirmed detectable HCV RNA (2 specimens, 1 week apart), then the participant has experienced a late HCV relapse or a recurrent infection.

- Question the participant about use of injection or inhalation drugs

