7.1.1.3 Withdrawal of Pembrolizumab only

Participants MAY be withdrawn from pembrolizumab for the following reasons:

• Participants who experience a delay of more than 12 weeks to receive the subsequent pembrolizumab infusion due to treatment-related toxicity or corticosteroids cannot be

Page 78 of 141

reduced to \leq 10 mg prednisone or equivalent per day within 12 weeks, according to dose modification guidance in Section 6.6.

- Unacceptable toxicity, i.e. event requiring permanent discontinuation of pembrolizumab according to dose modification guidance in Section 6.6.
- Discontinuation of pembrolizumab may be considered for participants who have attained a confirmed CR that have been received at least 8 infusions (24 weeks) of pembrolizumab and had at least 2 infusions with pembrolizumab beyond the date when the initial CR was declared.

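### Pembrolizumab restart guidance after a hepatitis B or C flare has no branch for a Grade 1 baseline ALT, so recovery to that baseline leads, read literally, to permanent discontinuation

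*Protocol*

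**What the plan says.** Table 6-6 (Protocol Section 6.6.2.1) gives separate pembrolizumab restart rules by cause of the hepatic event. For a hepatitis B flare, restart is allowed "only if ALT returns to normal or Grade 1 (if normal at baseline), or to baseline grade (if Grade 2 at baseline". For hepatitis C recurrence or flare it is allowed "only if ALT returns to normal or G1 (if normal at baseline), or to baseline grade (if G2 at baseline". Both bullets add a 12-week limit and clinical stability, and both end by sending every other case to permanent discontinuation.

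Sites are routed to these bullets. The general instructions of Table 6-5 (Section 6.6.2) refer hepatitis B and C flares to Table 6-6, and the ALT/AST rows refer the pembrolizumab restart decision there too.

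The protocol also limits the force of the tables. Section 6.6 says the recommendations "can be used as support for the clinical decision and respective monitoring". Table 6-5 repeats that those on "dose adjustments and treatment interruptions can be used as support for the clinical decision". Section 7.1.1.3 opens with "Participants MAY be withdrawn from pembrolizumab for the following reasons".

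**The concern.** The bullets are built as a closed rule: restart under the named conditions, otherwise stop. Two baseline categories are named, normal and Grade 2. The category between them is not, so it falls to the default.

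A site that follows the text literally takes a recovered, stable participant off pembrolizumab. A site that uses its judgement restarts. Pembrolizumab exposure and discontinuation counts could then differ by site for the same clinical course. Dose modification, including discontinuation, is a secondary safety endpoint (Protocol Section 3, Table 3-1), and the SAP tabulates adverse events that lead to discontinuation of pembrolizumab (Section 5.4.1.2).

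**Working it through.** The plan states no figure on this point, so the check is a case enumeration, followed by an illustration of size.

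**1. Can a participant with a Grade 1 baseline ALT enrol?** Table 5-1 (Section 5.1) allows AST and ALT up to 5.0 × ULN. Inclusion criterion 11 admits controlled hepatitis B, and criterion 12 says "Participants may have a past or ongoing hepatitis C virus (HCV) infection". The documents cite CTCAE v5.0 for grading but do not print the ALT cut-offs. That Grade 1 baselines occur is therefore inferred from the 5.0 × ULN ceiling and from the presence of a Grade 2 clause in the bullets.

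**2. Can such a participant reach the rule?** Table 6-6 describes hepatitis B flares by "rapid elevations of ALT and AST to >5 × ULN and/or >3 × baseline". The hepatitis C description uses the same thresholds together with a rise in HCV RNA. The second threshold is relative to the participant's own level, so a raised baseline does not prevent a flare from being declared.

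**3. What does the rule say in each case?** The phrase about a normal baseline can be read in two ways. In reading A it qualifies both recovery levels, normal and Grade 1. In reading B it qualifies Grade 1 only. For a clinically stable participant within 12 weeks:

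| Baseline ALT | Recovers to | Reading A | Reading B |
|---|---|---|---|
| Normal | Normal or Grade 1 | Restart | Restart |
| Grade 1 | Normal | Discontinue | Restart |
| Grade 1 | Grade 1 | Discontinue | Discontinue |
| Grade 2 | Grade 2 | Restart | Restart |

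Full recovery to a Grade 1 baseline ends in discontinuation under both readings. The outcome is also out of order: ending at Grade 2 from a Grade 2 baseline permits restart, while ending at Grade 1 from a Grade 1 baseline does not.

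**4. Does another rule supply the missing branch?** Three rules nearby are worded more completely:
- Immune-related hepatitis (Table 6-6) accepts Grade 1 or lower, or baseline where that was abnormal. It applies only after viral flare has been ruled out.
- Other causes (Table 6-6) names normal and Grade 1 starting values together. It is headed for different causes.
- The general Grade 2 row of Table 6-3 (Section 6.6) reads "Restart at same dose if resolution to ≤ G1 or baseline ≤ 12 weeks of last infusion", and the general Grade 3 row uses the same recovery standard. These rows are not specific to viral flare, for which Table 6-5 points to Table 6-6.

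They show the protocol's usual standard, but none states it for a viral flare.

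**5. How many participants?** The documents give no viral-hepatitis share, Grade 1 ALT share or flare rate. All three inputs below are assumptions: 30–70% with hepatitis B or C, 20–60% of those with a Grade 1 baseline ALT, and 2–10% of those flaring.

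Flares in Grade 1 baselines = N × viral share × Grade 1 share × flare risk

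- Planned total, N = 119: 119 × 0.30 × 0.20 × 0.02 = 0.14; 119 × 0.70 × 0.60 × 0.10 = 5.0 (0.1% to 4.2%).
- Pilot phase, N = 52: 52 × 0.30 × 0.20 × 0.02 = 0.06; 52 × 0.70 × 0.60 × 0.10 = 2.2.

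For these inputs the counts are too high as an estimate of those affected. Only participants who recover to Grade 1 rather than to normal, in time and clinically stable, meet the gap under both readings. The SAP Version History also records that recruitment stopped early.

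**The case against.** The strongest reply is that the harm needs a reading the protocol discourages. The tables are guidance, the investigator decides on all clinical information, and hepatitis B flares are to be managed with a hepatologist. Section 7 makes the same point by contrast: Section 7.1.1.2 uses *must* for withdrawal of regorafenib, Section 7.1.1.3 uses *MAY* for pembrolizumab, and Section 7.1.1.1 leaves withdrawal for abnormal liver function to the investigator's consideration. The intent is also easy to infer, since the literal result is anomalous and the neighbouring rules all accept return to baseline. Finally, the size illustration rests on assumptions throughout and spans about 36-fold. Flares should also be limited by the viral-load and antiviral requirements at entry, and late hepatitis C relapse is described as rare.

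Most of this stands as a limit on impact. It does not fill the gap. Discretion is how two sites could reach opposite decisions on one clinical course, and the investigator who looks for the restart rule is sent to the incomplete bullets. Section 7.1.1.3 itself refers back to Section 6.6 for which events require permanent discontinuation. That sites would actually differ is a possibility, not something the documents show.

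**Conclusion.** The concern holds. Both viral-flare bullets omit a Grade 1 baseline ALT. Read literally, they direct a participant who has recovered to that baseline off pembrolizumab, while the categories on either side may restart. It is a wording gap in advisory text and not a flaw in the design.

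The effect is small and cannot be quantified from the documents; the range of 0.14 to 5.0 of 119 is an illustration on the high side for its assumed inputs. The conclusion on the text needs no assumption beyond some participants having a Grade 1 ALT at entry. Sample size, alpha, power and the planned response-rate test do not change. The correction is worth making because the default is permanent loss of study drug and the remedy is nearly free.

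**What to change.** In the hepatitis B and hepatitis C restart bullets of Table 6-6, extend the first parenthesis so that recovery to normal or Grade 1 suffices when the baseline was normal *or Grade 1*. Leave the Grade 2 clause, the 12-week limit, the stability condition and the discontinuation default as they are. The same pairing of normal and Grade 1 already appears in the rule for other causes in that table.

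With this change, a Grade 1 baseline that recovers to Grade 1 moves from discontinuation to restart allowed. Recovery from Grade 1 to normal is allowed under either reading, and the normal and Grade 2 outcomes stay the same. The cost is a few words in two bullets, with no change to design, sample size or analysis.

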Gastrointestinal bleeding suggestive of portal hypertension (e.g., esophageal or gastric varices)	Discontinue and assess according to guidance given in Table 6–6	Hold and assess + decide on potential restart according to guidance given in Table 6–6
Recurrence of a severe or life-threatening event, or of any of the laboratory abnormalities listed above	Discontinue and assess according to guidance given in Table 6–6	Discontinue and assess according to guidance given in Table 6–6
If the participant is off study treatment therapy for infection, obstruction, or drug/alcohol-related toxicity for more than 3 weeks, or if they have esophageal bleeding, or become CP C at any point	Discontinue and assess according to guidance given in Table 6–6	Discontinue and assess according to guidance given in Table 6–6

 $ALT = alanine\ aminotransferase;\ AST = aspartate\ aminotransferase;\ G1/2/3/4 = Grade\ 1/2/3/4;\ QD = every\ day;\ ULN = upper\ limit\ of\ normal$

a: If reductions are required resulting in a dose of less than 60 mg QD of regorafenib, then regorafenib will be permanently discontinued. For Grade 3 neutropenia, the participant could stay on regorafenib for the first appearance, or hold until resolved to Grade 2 or less, restart at the same dose level or lower after discussion between the investigator and the sponsor.

b: Hold until recovery to Grade ≤ 1 and restart at the same dose level or reduce 1 dose level a (at the investigator's discretion) if hepatic encephalopathy is manageable and reversible, after discussion with the sponsor.

Page 67 of 141

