- At the time of first detection of HCV RNA, send a specimen for HCV genotyping or serotyping (if genotyping is not available) (local laboratory)
- Measure AST, ALT, ALP, Tbil, Dbil, and INR weekly
- Measure HCV RNA levels every 2 weeks
- Therapy with HCV antiviral treatments should be strongly considered.

HCV Flare (hepatitis C exacerbation in participants with HCV RNA positive):

 At the time of first detection of HCV RNA, send a specimen for HCV genotyping or serotyping (if genotyping is not available) (local laboratory)

Page 69 of 141

Table 6–6: Guidance on Assessment and Further Dosing Following Occurrence of Hepatic Events of Clinical Interest

- Measure AST, ALT, ALP, Tbil, Dbil, INR weekly
- Measure HCV RNA levels every 2 weeks
- Therapy with HCV antiviral treatments should be strongly considered

Further information concerning Immune-related hepatitis

Description: Immune-related hepatitis due to study treatment should be suspected if any of the following is seen:

- ALT baseline values are less than 2 × ULN, and AST or ALT laboratory values increase to ≥5 × ULN
- Among participants with baseline ALT ≥2 × ULN, levels increase to >3× the baseline level
- ALT >500 U/L regardless of baseline level
- Total bilirubin >3.0 mg/dL regardless of baseline level

Immune-related hepatitis is a diagnosis made after excluding other possible etiologies for the change. Viral flare (if applicable), biliary or vascular obstruction, infection, medications, and alcohol use must be ruled out (see below).

Management:

- Interrupt pembrolizumab intervention for up to 12 weeks
- Start IV corticosteroid (60 mg/day of prednisone or equivalent) followed by oral corticosteroid
 - Monitor with biweekly laboratory tests including AST, ALT, Tbil, Dbil, ALP, and INR
 - Restart pembrolizumab intervention only if:
 - Abnormal laboratory values resolve to Grade ≤1 or baseline (if abnormal at baseline)
 - Taper steroid over 28 days
 - Steroid treatment is tapered to prednisone <10 mg/day or equivalent
 - Permanently Discontinue pembrolizumab intervention if:
 - Laboratory abnormalities do not resolve within 3 weeks
 - Steroids cannot be lowered to ≤10 mg/day (or prednisone equivalent) within 12 weeks
 - o Evidence of decompensation to CP C status

Further information concerning other causes:

- Rule out infection with blood, urine and ascites culture antibiotics should be started if infection is found

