- If total bilirubin is elevated, imaging should be obtained to rule out vascular compromise, biliary obstruction, and/or tumor progression by imaging. If biliary obstruction is present, consultation with a gastroenterologist and/or an interventional radiologist should be obtained to see if the obstruction may be relieved.
- · Ruled out alcohol use and hepatotoxic drugs including herbal and alternative medications
- Interrupt pembrolizumab intervention for up to 12 weeks
- Restart pembrolizumab only if laboratory values have returned to Grade 1 or baseline (if normal or Grade 1 at start) or to baseline grade within 3 weeks

AE = adverse event; ALP = alkaline phosphatase; ALT = alanine aminotransferase; anti-HBc = Hepatitis B core antibody; anti-HBe = hepatitis B e-antigen; anti-HBs = hepatitis B surface antibody; AST = aspartate aminotransferase; CP = Child-Pugh (score); Dbil = direct bilirubin; dL = deciliter; DNA = deoxyribonucleic acid; G1/2/3/4 = Grade 1/2/3/4; GGT = gamma-glutamyl transferase; HBeAg = Hepatitis B e-antigen; HBsAg = hepatitis B surface antigen; HBV = hepatitis B virus; HCV = hepatitis C virus; IV = intravenous; IgM = Immunoglobulin M; INR = international normalized ratio; mg = milligram; RNA = ribonucleic acid; SAE = serious adverse event; SVR = sustained viral response; Tbil = total bilirubin; ULN = upper limit of normal

6.6.3 Dose Modification and Toxicity Management for Immune-related AEs Associated with Pembrolizumab

AEs associated with pembrolizumab exposure may represent an immunologic etiology. These irAEs may occur shortly after the first dose or several months after the last dose of pembrolizumab treatment and may affect more than one body system simultaneously. The irAEs may be fatal and may occur after discontinuation of pembrolizumab. Therefore, early recognition and initiation of treatment is critical to reduce complications. Based on existing clinical trial data, most irAEs were reversible and could be managed with interruptions of pembrolizumab, administration of corticosteroids and/or other supportive care. For suspected irAEs, ensure adequate evaluation to confirm etiology or exclude other causes. Additional procedures or tests such as bronchoscopy, endoscopy, skin biopsy may be included as part of the evaluation. Based on the severity of irAEs, withhold or permanently discontinue pembrolizumab and administer corticosteroids.

Table 6-7: Dose Modification Guidance, Other Immune-related Adverse Events

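### For liver events due to infection, obstruction or drug/alcohol toxicity, Table 6-6 lets pembrolizumab be held for up to 12 weeks while Table 6-5 says to discontinue after more than 3 weeks off treatment

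*Protocol*

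**What the plan says.** **Table 6-6, block on other causes (Protocol Section 6.6.2.1).** This block covers infection, vascular compromise, biliary obstruction, tumor progression, alcohol and hepatotoxic drugs. It has two timing lines. The first is "Interrupt pembrolizumab intervention for up to 12 weeks". The second permits restart only if laboratory values "have returned to Grade 1 or baseline (if normal or Grade 1 at start) or to baseline grade within 3 weeks". The block has no steroid criterion, and it does not say what happens to a participant who misses the 3-week limit.

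**Table 6-5, last row (Section 6.6.2).** The trigger is: "If the participant is off study treatment therapy for infection, obstruction, or drug/alcohol-related toxicity for more than 3 weeks". Both drug columns then say to discontinue and to assess under Table 6-6.

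**Table 6-6, immune-related hepatitis.** The same 12-week hold applies. Pembrolizumab stops permanently if "Laboratory abnormalities do not resolve within 3 weeks" or if "Steroids cannot be lowered to ≤10 mg/day (or prednisone equivalent) within 12 weeks", and the restart conditions include "Taper steroid over 28 days".

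**Table 6-6, HBV and HCV flares.** The hold and the recovery limit are both 12 weeks, and failure to recover means permanent discontinuation.

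Neither the block on other causes nor the Table 6-5 row says when its clock starts.

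**The concern.** Infection, obstruction and drug or alcohol toxicity appear in both tables. One table tolerates a pembrolizumab hold four times as long as the time off treatment at which the other says to discontinue (12 / 3 = 4). The Table 6-5 row also sends the site to Table 6-6, so both rules reach the same participant.

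Two sites could therefore handle the same event differently, each with a table to cite. Section 2.3.1 gives liver toxicity special importance. Section 6.6.2 reports Grade 3 AST or ALT increases in 31% of patients in the Phase 1b study of the combination, though the share due to these non-immune causes is not given. On the analysis side, SAP Section 5.4.1.2 tabulates adverse events leading to discontinuation and to interruption, by drug, so which table a site follows can change those counts. Sample size, alpha and power are not affected.

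**Working it through.** The plan states no figure to reproduce, so this check sets the rules side by side and does the week arithmetic.

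**Inputs**
- Permitted pembrolizumab hold, other causes: 12 weeks (Table 6-6).
- Laboratory recovery limit for restart, other causes: 3 weeks (Table 6-6).
- Time off treatment that triggers discontinuation: more than 3 weeks (Table 6-5, last row).
- Pembrolizumab interval: 6 weeks (Section 4.1.1.2).
- Steroid taper, immune-related hepatitis only: 28 days = 28 / 7 = 4 weeks (Table 6-6).

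**Step 1: can a 3-week and a 12-week limit coexist?** In immune-related hepatitis they can. Recovery at the latest permitted time, followed by the taper, ends at 3 + 4 = week 7, inside 12 weeks. HBV and HCV flares carry a single limit. The block on other causes has no taper or other criterion to separate the two figures.

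**Step 2: the two tables by case, for infection, obstruction or drug/alcohol toxicity**

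| Case | Table 6-6, other causes | Table 6-5, last row | Result |
|---|---|---|---|
| Values recover by week 3, back on treatment by week 3 | Restart allowed | Not triggered | Agree |
| Values recover by week 3, off treatment for more than 3 and up to 12 weeks | Restart allowed | Discontinue | Conflict, if the row covers a hold of pembrolizumab alone |
| Values recover after week 3 | Hold allowed, restart not allowed | Discontinue once off for more than 3 weeks | No further infusion under either |

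The stretch of hold that one table permits and the other does not is 12 − 3 = 9 weeks. A clash over restart arises only in the second case. In the third, the hold has no stated purpose after week 3.

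**Step 3: does 6-weekly dosing produce the second case?** Let t be the weeks from the last infusion to onset of the event. The next scheduled infusion falls 6 − t weeks after onset, which is more than 3 weeks whenever t < 3.

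- *Illustration A: t = 1, recovery 2 weeks after onset.* The next infusion is due 6 − 1 = 5 weeks after onset. Table 6-6 is satisfied (2 ≤ 3 and 5 ≤ 12). Under Table 6-5, a clock from onset gives 5 weeks, so discontinue. A clock from the first missed infusion gives 0, since none was missed. A clock from the last infusion gives 6 weeks, which every participant reaches on the normal schedule, so that reading cannot be the intended one.
- *Illustration B: t = 5, recovery 2 weeks after onset, at week 7 from the last infusion.* The infusion due at week 6 is withheld. Given on recovery, it is 7 − 6 = 1 week late. If the site waits for the next slot at week 12, the delay is 12 − 6 = 6 weeks from the missed date, or 12 − 5 = 7 weeks from onset. Both exceed 3 weeks and both lie within 12. The block does not say which course a site should take.

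**Step 4: one drug or both?** Suppose that in either illustration regorafenib is held at onset and resumes on recovery. The participant has then been off both drugs for 2 weeks. If the Table 6-5 row means both drugs, it is not triggered; if it includes pembrolizumab alone, it can be. The row does not say.

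**The case against.** A reader might infer that anyone recovering between weeks 3 and 12 gets opposite decisions. The documents do not support that: after late recovery Table 6-6 bars restart and Table 6-5 says discontinue, so neither leads to another infusion. A reader might also infer that a 12-week hold is by definition more than 3 weeks off study treatment. That goes too far. Section 4.1.1.2 lets one drug continue while the other is interrupted for toxicity, and several Table 6-5 rows resume regorafenib at a reduced dose after recovery. Both objections stand, and they narrow the point to the second case above, with its condition.

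Three further objections stand in part.
- *The tables are guidance.* Sections 6.6 and 6.6.2 describe them as support for the investigator's decision, and Section 7.1.1.3 lists pembrolizumab-only withdrawal as something that may be done. This softens the conflict without resolving it: discretion still needs a coherent starting rule, and Section 7.1.1.2 makes withdrawal from regorafenib mandatory when Section 6.6 requires its permanent discontinuation.
- *Steroids may have been started anyway.* The Table 6-5 general instructions call for corticosteroids in some Grade 3/4 liver abnormalities, possibly before a non-immune cause is found. So it cannot be said that these participants never receive steroids, only that the block on other causes ties neither limit to them.
- *The endpoint effect is small.* The secondary endpoint counts participants with any dose modification, and interruption already qualifies. Only the split between interruption and discontinuation can move.

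The lists of causes also differ: vascular compromise and tumor progression appear only in Table 6-6, so the point is confined to the shared causes.

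**Conclusion.** The point holds in a narrow form. For the shared causes, Table 6-6 and the last row of Table 6-5 disagree about a participant whose values recover within 3 weeks but who remains off treatment for more than 3 and up to 12 weeks, a 9-week range. This rests on one assumption that the protocol neither confirms nor excludes: that being off study treatment includes a hold of pembrolizumab alone. The undefined clock start adds to the uncertainty, since the same course can count as 0 or 5 weeks off treatment. For recovery after week 3 the defect is smaller: a permitted hold that cannot lead to restart.

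The immune-related hepatitis limits and the viral flare limits are not part of the conflict. The documents give no frequency for these events, so the number of participants affected cannot be estimated. The effect is on consistency of safety management and on the interruption and discontinuation tables.

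**What to change.** Reconcile the last row of Table 6-5 with the block on other causes in Table 6-6. For each limit, state three things:
- whether it times laboratory recovery or time off drug;
- when the clock starts;
- whether being off study treatment means one drug or both.

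The block on other causes should also say what a hold beyond week 3 is for and what follows if values have not recovered by then. Which limit is right is a clinical decision for the sponsor, and none is proposed here. The cost is wording in two tables, with no change to the design, the sample size or the analysis methods.
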